8.6 Definition of End of Study

The expected duration of the study is 18 months from recruitment of the first participant. The end of study is 6 months following the date of the last visit of the last participant.

9. Recording and reporting of adverse events

9.1 Definitions	
-----------------	--

Term	Definition	
Adverse Event (AE)	Any untoward medical occurrence in a patient or trial participant, which does not necessarily have a causal relationship with the intervention involved.	
Serious Adverse Event	Any adverse event that:	
(SAE).	□ results in death	
	□ is life-threatening*	
	requires hospitalisation or prolongation of existing hospitalisation**	
	□ results in persistent or significant disability or incapacity, or	
	□ consists of a congenital anomaly or birth defect.	
* A life- threatening event, this refers to an event in which the participant was at risk of death at		

* A life- threatening event, this refers to an event in which the participant was at risk of death at the time of the event; it does not refer to an event which hypothetically might have caused death if it were more severe.

** Hospitalisation is defined as an in-patient admission, regardless of length of stay. Hospitalisation for pre-existing conditions, including elective procedures do not constitute an SAE.

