6.2 Exclusion Criteria

- 1. Painful or acute perianal conditions: fissures/perianal abscess/recent trauma
- 2. Anal cancer
- 3. Anorectal surgery in the last 3 months

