9.4 Procedures for recording and reporting Serious Adverse Events

All serious adverse events will be recorded in the medical records and the CRF, and the sponsor's AE log. The AE log of SAEs will be reported to the sponsor at least once per year.

All SAEs must be recorded on a serious adverse event (SAE) form. The PI or designated will complete the sponsor's SAE form and the form will be emailed to the Sponsor within 5 working days of becoming aware of the event. The Chief or Principal Investigator will respond to any SAE queries raised by the sponsor as soon as possible.

Where the event is unexpected and thought to be related to the intervention, this must be reported by the Investigator to the Health Research Authority within 15 days.

Completed SAE forms must be sent within 5 working days of becoming aware of the event to the Sponsor Email forms to [contact]

SAEs will be reported to the sponsor until the end of the trial.

Participants must be followed up until clinical recovery is complete. Follow-up SAE forms (clearly marked as follow-up) should be completed and emailed to the JRO as further information becomes available.

Flow Chart for SAE reporting

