11.3 Sample size calculation

The sample size has not been formally calculated at this time. This is due to no previous studies on this area being performed. A pilot study to identify the 'normal' measurements for the MAPLe stipulated 30 participants per group to identify a statistically significant result. Accounting for 4 participant groups a sample size of 120 has been set.

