11.5 Statistical analysis

11.5.1 Primary outcome analysis

Non-inferiority testing of MAPLe will be performed using Bland-Altman method. Correlation between MAPLe and AUS for location of sphincter abnormality will be identified. Correlation between MAPLe and HRAM for functional abnormalities will be identified.

Participants will be allocated a patient group dependent on the cause of FI:

- □ Fistula/ chronic perianal conditions
- \Box Obstetric injury <12 months
- \Box Obstetric injury > 12 months
- □ Neuropathic

Each group will be analysed using correlation studies and regression analysis to determine which groups benefit from MAPLe assessment.

The clinical benefit of the addition of MAPLe assessment will be determined from the analysis of the results of the expert panel.

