13.1 Trial Management Group (TMG)

The TMG will include the Chief Investigator and trial staff. The TMG will be responsible for overseeing the trial. The group will meet regularly, once per week at each site and will send updates to PIs.

The TMG will review recruitment figures, SAEs and substantial amendments to the protocol prior to submission to the REC. All PIs will be kept informed of substantial amendments through their nominated responsible individual.

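### The SAE footnote excludes all admissions for pre-existing conditions, so an unplanned admission for worsening perianal disease after the session can be classed as non-serious and bypass the 9.4 reports

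*Combined protocol and SAP*

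**What the plan says.** Section 9.1 lists the seriousness criteria. One is that the event "requires hospitalisation or prolongation of existing hospitalisation", and this criterion carries a footnote. The footnote first sets a broad meaning: "Hospitalisation is defined as an in-patient admission, regardless of length of stay". It then narrows the criterion: "Hospitalisation for pre-existing conditions, including elective procedures do not constitute an SAE".

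Two expedited reports depend on SAE status, and both are in section 9.4. One is the SAE form, due with the sponsor within 5 working days of awareness. The other reads "Where the event is unexpected and thought to be related to the intervention, this must be reported by the Investigator to the Health Research Authority", with a limit of 15 days. Section 13.1 adds a third consequence: "The TMG will review recruitment figures, SAEs and substantial amendments to the protocol prior to submission to the REC".

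On the population, section 11.5.1 names "Fistula/ chronic perianal conditions" as one of four analysis groups. Section 6.2 excludes "Painful or acute perianal conditions: fissures/perianal abscess/recent trauma".

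**The concern.** The usual purpose of such a footnote is to keep planned admissions out of the SAE count. This study has a good reason to want that, because participants may go on to surgery or an implanted neuromodulator (sections 8.4 and 11.5.2). The wording goes further. It removes any admission for a pre-existing condition, whether planned or not, whether or not the condition has worsened, and whatever the suspected link to the procedures.

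Here the pre-existing condition lies at the site where the probes are placed. A chronic perianal condition that worsens after the session is therefore the kind of event whose relation to the procedures the sponsor would want assessed quickly. Section 3.1 states that no additional risk is perceived from MAPLe. Safety reporting is the means of checking that statement while recruitment continues, and the footnote can weaken it for the participants to whom it matters most.

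**Working it through.** The plan gives no figure to reproduce, so the check is to read the sections against each other.

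**1. Scope of the exclusion.** The word introducing elective procedures makes them an included example, not the limit. Sections 9.2 to 9.8 contain no exception for unplanned admission, worsening or relatedness.

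**2. Who it can affect.** Faecal incontinence is an inclusion criterion (6.1), so all 120 participants have a pre-existing anorectal condition. Section 11.3 refers to a pilot study that "stipulated 30 participants per group". With four groups, 4 × 30 = 120, and the fistula/chronic perianal group is planned at 30/120 = 25%. This is a group size, not an event rate. The exclusion of acute perianal disease in 6.2 applies at entry. It does not cover chronic disease that worsens later.

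**3. Which events.** Death, life-threatening events and persistent or significant disability remain SAEs whatever the cause. The gap is confined to events that are serious only because of hospitalisation.

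**4. Effect on causality assessment.** The AE definition in 9.1 requires no causal link. Section 9.2.2 already deals with natural flares, since its middle category allows the participant's own condition to contribute. The footnote decides SAE status without reference to that assessment, so even an admission judged related can fall outside 9.4.

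**5. Effect on expedited reporting.** Section 9.2.3 lists no expected adverse events, so any related SAE is unexpected and falls under the 15-day rule. Whether the event is an SAE therefore decides whether that report is made.

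**6. What remains for an event classed as not an SAE.**

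| Route | Section | Recipient and timing |
|---|---|---|
| CRF entry | 9.3 | Study record; no reporting deadline |
| Device incident | 9.7 | Manufacturer if related to MAPLe, local Trust if AUS or HRAM; usually within 24 hours |
| Trust incident report | 9.8 | Trust, on awareness, if the incident definition is met |
| TSC review of adverse events | 13.2 | TSC; no meeting frequency stated |
| Site adverse event log | 15 | Sponsor, annually |

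The device route depends on attributing the event to one device. HRAM and MAPLe are performed in the same session, as is AUS at one site (8.3), so attribution may be uncertain. Urgent safety measures (9.5) and protocol violations (9.6) have their own short timelines, but an admission alone triggers neither. No remaining route takes the event to the sponsor or the Health Research Authority within days.

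**The case against.** The strongest reply is that the protocol itself separates acute from chronic perianal disease. Section 6.2 bars acute conditions at entry and names abscess among them. An eligible participant admitted with new perianal sepsis did not have that sepsis at entry, so an investigator can reasonably call it a new untoward occurrence and report an SAE. This stands, and it rules out the stronger reading that such an admission is necessarily not an SAE. It does not remove the defect. Nothing requires that classification, two sites could treat the same event differently, and the argument is weaker for plain worsening of a known fistula than for a new abscess.

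A second reply is that the event is not lost. It is recorded in the CRF, may reach the manufacturer or Trust quickly, and is open to TSC review. This also stands. A reader might infer that all expedited reporting is missed, or that the study could report no SAEs because its definition removed them. The documents support neither. The other seriousness criteria still apply, fast routes to the manufacturer and Trust exist, and all adverse events are recorded. What may be missed is the two reports in 9.4 and the TMG's review of SAEs.

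A third reply is that harm from the probe is not documented. Section 3.1 describes a recording device used in the same way as current ones, and section 15 rates the study low risk. That is fair. The point does not rest on the probe being harmful, only on whether a serious event would be reported promptly if one occurred.

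**Conclusion.** The concern holds in a limited form. The footnote is ambiguous in a way that allows an unplanned admission for worsening of a pre-existing anorectal condition to be classed as not an SAE. Such an event may bypass the 5-working-day sponsor form, the 15-day Health Research Authority report and TMG review.

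The conclusion rests on two conditions: hospitalisation is the event's only seriousness criterion, and the site reads the admission as being for the pre-existing condition. The size cannot be put as a number of events, because the documents give no admission or event rate. The figure of 30 in 120 shows only how many participants are planned for the group most directly concerned. If the annual log were the sponsor's only source, notification could take up to about 12 months instead of 5 working days. That is the worst case on one route, not an expected delay. The sample size and the planned efficacy and agreement analyses are unaffected.

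**What to change.** Reword the footnote in 9.1 so that only a planned (elective) admission for a condition that was present before consent and has not worsened is excluded. State that an unplanned admission, or an admission for worsening of a pre-existing condition including faecal incontinence, fistula or other perianal disease, is an SAE and goes through the causality assessment in 9.2.2. Put the same sentence in the SAE form guidance so that both sites classify alike, and check that 9.4 and 9.7 read consistently with it.

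The cost is one sentence in the protocol, the matching guidance, and a few extra SAE forms. Some of these will be for natural flares judged not related. Planned admissions for surgery or device implantation stay outside the definition provided the condition has not worsened, so the footnote keeps its legitimate purpose.

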9.2 Assessments of Adverse Events

Each adverse event will be assessed for severity, causality, seriousness and expectedness as described below.

Category	Definition
Mild	The adverse event does not interfere with the participant's daily routine, and does not require further intervention; it causes slight discomfort
Moderate	The adverse event interferes with some aspects of the participant's routine, or requires further intervention, but is not damaging to health; it causes moderate discomfort
Severe	The adverse event results in alteration, discomfort or disability which is clearly damaging to health

9.2.1 Severity

9.2.2 Causality

The assessment of relationship of adverse events to the intervention is a clinical decision based on all available information at the time of the completion of the case report form.

The following categories will be used to define the causality of the adverse event:

Category	Definition
Definitely:	There is clear evidence to suggest a causal relationship, and other possible contributing factors can be ruled out.
Probably:	There is evidence to suggest a causal relationship, and the influence of other factors is unlikely
Possibly	There is some evidence to suggest a causal relationship (e.g. the event occurred within a reasonable time after administration of the trial intervention). However, the influence of other factors may have contributed to the event (e.g. the participant's clinical condition, other concomitant events).
Unlikely	There is little evidence to suggest there is a causal relationship (e.g. the event did not occur within a reasonable time after administration of the trial intervention). There is another reasonable explanation for the event (e.g. the participant's clinical condition, other concomitant treatments).
Not related	There is no evidence of any causal relationship.
Not Assessable	Unable to assess on information available.

9.2.3 Expectedness

There are no expected adverse events.

9.3 Recording adverse events

All Adverse events will be recorded in the CRF following consent.

9.4 Procedures for recording and reporting Serious Adverse Events

All serious adverse events will be recorded in the medical records and the CRF, and the sponsor's AE log. The AE log of SAEs will be reported to the sponsor at least once per year.

All SAEs must be recorded on a serious adverse event (SAE) form. The PI or designated will complete the sponsor's SAE form and the form will be emailed to the Sponsor within 5 working days of becoming aware of the event. The Chief or Principal Investigator will respond to any SAE queries raised by the sponsor as soon as possible.

Where the event is unexpected and thought to be related to the intervention, this must be reported by the Investigator to the Health Research Authority within 15 days.

Completed SAE forms must be sent within 5 working days of becoming aware of the event to the Sponsor Email forms to [contact]

SAEs will be reported to the sponsor until the end of the trial.

Participants must be followed up until clinical recovery is complete. Follow-up SAE forms (clearly marked as follow-up) should be completed and emailed to the JRO as further information becomes available.

Flow Chart for SAE reporting

9.5 Reporting Urgent Safety Measures

If any urgent safety measures are taken the CI/ PI shall immediately and in any event no later than 3 days from the date the measures are taken, give written notice to the relevant REC and Sponsor of the measures taken and the circumstances giving rise to those measures.

9.6 Notification of reportable protocol violations

A reportable protocol violation is a breach which is likely to effect to a significant degree:

- □ the safety or physical or mental integrity of the participants of the study; or
- \Box the scientific value of the study.

The sponsor will be notified immediately of any case where the above definition applies during the trial conduct phase.

9.7 Reporting incidents involving a medical device

All adverse event reporting will be undertaken by a study representative. If the event is in relation to MAPLe the event will be reported to the manufacturer Medtronic via the Sales support worker [name].

Adverse events involving routine devices, AUS and HRAM, will be reported locally within each trust in accordance with local trust guidelines.

All incidents will be reported as soon as possible (usually within 24 hours).

9.8 Trust Incidents and Near Misses

An incident or near miss is any unintended or unexpected event that could have or did lead to harm, loss or damage that contains one or more of the following components:

- a) It is an accident or other incident which results in injury or ill health.
- b) It is contrary to specified or expected standard of patient care or service.
- c) It places patients, staff members, visitors, contractors or members of the public at unnecessary risk.
- d) It puts the Trust in an adverse position with potential loss of reputation.
- e) It puts Trust property or assets in an adverse position or at risk.

Incidents and near misses must be reported to the Trust through DATIX as soon as the individual becomes aware of them.

A reportable incident is any unintended or unexpected event that could have or did lead to harm, loss or damage that contains one or more of the following components:

- a) It is an accident or other incident which results in injury or ill health.
- b) It is contrary to specified or expected standard of patient care or service.
- c) It places patients, staff members, visitors, contractors or members of the public at unnecessary risk.
- d) It puts the Trust in an adverse position with potential loss of reputation.
- e) It puts Trust property or assets in an adverse position or at risk of loss or damage.

10. Data management

10.1 Confidentiality

All data will be handled in accordance with the UK Data Protection Act 2018.

The Case Report Forms (CRFs) will not bear the participant's name or other personal identifiable data. The study identification number will be used for identification and this will be clearly explained to the patient in the PIS. Patient consent for this will be sought.

10.2 Data collection tools and source document identification

Data will be collected from sites on study specific case report forms (CRFs) or data collection tools such as electronic CRFs.

Source data are contained in source documents and must be accurately transcribed on to the CRF. All data will be recorded in the local notes and CRF.

All data required for the study will be obtained during the anorectal physiology session, minimising the risk of incomplete data sets.

10.3 Completing Case Report Forms

All CRFs must be completed and signed by staff that are listed on the site staff delegation log and authorised by the CI/ PI to perform this duty. The CI/PI is responsible for the accuracy of all data reported in the CRF.

Once completed CRFs will remain within each parent trust and stored in a designated locked filing cabinet. They will not be removed from their trust site.

10.4 Data handling

The study is compliant with the requirements of General Data Protection Regulation (2016/679) and the Data Protection Act (2018). All investigators and study site staff will comply with the requirements of the General Data Protection Regulation (2016/679) with regards to the collection, storage, processing and disclosure of personal information, and will uphold the Act's core principles. UCL is the data controller; the UCL Data Protection Officer is [name] [contact]. The data processors are the Student Researcher and the Chief Investigator. The study will be collecting the following data: Age, gender, parity, medical and surgical history, drug history.

Once a participant is enrolled, they will be allocated an individual study number. No record of name/date of birth/address/telephone number will be made. A list of individual study number and associated hospital numbers will be recorded in an encrypted database on a computer within each trust. The list will only comprise of participants recruited from that trust. Data will be provided directly by the participants and recorded on a CRF by the student investigator. Investigation results will be recorded on the CRF. The CRF will not record personal data. The CRF and completed questionnaires will be stored in a locked filing cabinet in the GI physiology department at each trust only accessible to study personnel. The anonymised research data will be collated by the student researcher in an encrypted database on each trust computer. For analysis, a copy of the research data obtained at ASPH will be made and placed on an encrypted USB. This will be transferred to UCLH and combined with the research data from this site. This will be undertaken by the student researcher. The CRF and associated documents will be destroyed 2 years following completion of study by their trust. The electronic database will be stored for 5 years.

11. Statistical Considerations

11.1 Primary Outcome

They primary outcome is to determine which participant groups benefit from assessment with MAPLe. Benefit will be determined by correct identification of abnormalities in symptomatic participants using MAPLe, correlation between symptom profile and MAPLe results, and the outcome of the expert panel. It will be measured once the end of recruitment is reached.

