FI is a symptom requiring structural and functional assessment of the anal sphincter to direct choice of treatment. Structural assessment using AUS has been proven to be sensitive(12)(29). Functional assessment can result in a disparity between symptom profile and investigation findings(30) as well as an overlap of results between healthy and symptomatic persons(31). This was shown by Lam et al who identified no correlation between ARP and FI scores in a study of 218 patients. These findings were also reflected in a study undertaken by Zutshi et al on 53 symptomatic females(28). The role of investigatory tests is to guide treatment(30) and although these tests can establish a baseline , both HRAM and AUS are poor predictors of treatment outcome(32). This identifies a need for further study into the assessment of FI.

Novel techniques investigating other properties of the anal canal have been developed. These include assessing elasticity of the anal canal and anal acoustic reflectivity. These techniques are in their early stages and studies so far have shown limited clinical utilisation(33).

Electromyography (EMG) is a technique used to assess the innervation and response of a voluntary muscle fibre to a stimulus. Traditionally EMG is performed using a single needle electrode inserted into a muscle. Following stimulus to voluntarily contract, an action potential is generated along a somatic nerve resulting in a synapse at the neuromuscular junction (NMJ), also called innervation zone, and the release of acetylcholine (ACh). ACh acts on voltage gated channels in the sarcolemma causing depolarisation from the resting potential of -60—90 mV to + 75mV (motor unit potential) resulting in contraction of the muscle fibre. The EMG needle electrode detects the depolarization and records the amplitude (mV) and frequency (Hz). This provides information on individual motor unit potentials resulting from the innervation zone but limited information on overall muscular function. EMG of the EAS requires multiple circumferential punctures into the muscle this is both invasive and painful, limiting the investigation to research and specialist cases.

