The role of sEMG in clinical assessment of FI has been limited to research and has not been correlated with current gold standard techniques. This study aims to investigate the sEMG of symptomatic patients using MAPLe. The study will test the non-inferiority of MAPLe against HRAM and AUS in assessing FI. Non-inferiority of a test is defined as the test being no worse than the competitor. The study will aim to identify if particular patient groups have closer correlation

between symptom profiles and FI scores and sEMG results, and whether sEMG improves following treatment. The study will endeavor to identify the clinical utilisation of sEMG in FI.

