3.1 Assessment and Management of Risk

The table below summarise the risks and mitigations of all test above standard care that are being performed in a table:

Intervention	Potential risk	Risk Management
Assessment with MAPLe device	The device will be placed anally and record sEMG, not providing stimulation. As the device will be used in the same nature as current assessment devices no additional risk is perceived.	Performed by trained operator.

4. Objectives

Primary: To determine the role of MAPLe in the assessment of FI in defined patient groups.

Secondary: To determine if targeted treatment is achieved following assessment with MAPLe.

5. Trial design

This is cohort study of participants with symptoms of faecal incontinence. It will take place across two hospital trusts, both able to provide specialist pelvic floor services and facilities required to meet the needs of the study and follow up required by the participants. The use of two sites aims to increase the yield and diversity of participants. The sample size for the study is 120 participants.

Following a stringent selection and recruitment process, participants will be invited to a designated ARP session where they will be consented, complete an incontinence and quality of life questionnaire, and undergo ARP assessment. This will comprise of the current gold standard, AUS and HRAM, and additional assessment with MAPLe using a standardised protocol. Through undertaking all three tests participants will act at their own controls. Participant participation will conclude following ARP assessment unless treatment is deemed necessary by their local MDT. These participants will be followed up at 6 months with interval MAPLe assessment and incontinence and quality of life questionnaire.

The results will undergo statistical analysis to determine non-inferiority of MAPLe in assessing FI. For analysis participants will be allocated to the following groups: fistula/chronic perianal conditions, obstetric injury <12 months, obstetric injury >12months, neurogenic. Each group will be analysed using symptoms profile and MAPLe results to identify correlation. Comparison of MAPle results pre and post treatment will determine if targeted treatment has been achieved.

An expert panel of pelvic floor specialists will be formed to determine the additional benefit of MAPLe in a clinical context. The panel will consist of 3-6 specialists within the field. To reduce bias,

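### The symptom-correlation part of the primary outcome uses MAPLe alone, so it cannot show how MAPLe compares with HRAM in tracking symptoms

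*Combined protocol and SAP*

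**What the plan says.** Section 11.1 gives benefit three components: correct identification of abnormalities by MAPLe, then "correlation between symptom profile and MAPLe results, and the outcome of the expert panel". Section 5 repeats the symptom component in the same single-test form: "Each group will be analysed using symptoms profile and MAPLe results to identify correlation". The Rationale in section 3 says "The study will aim to identify if particular patient groups have closer correlation" between symptoms or FI scores and sEMG. That is a contrast between patient groups, not between tests.

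HRAM enters section 11.5.1 as a test set against MAPLe. There is a Bland-Altman comparison, and "Correlation between MAPLe and HRAM for functional abnormalities will be identified". The same section adds "Each group will be analysed using correlation studies and regression analysis to determine which groups benefit from MAPLe assessment", without naming variables. Section 5 also gives HRAM results to the expert panel.

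The comparative aim is in the Rationale: "The study will test the non-inferiority of MAPLe against HRAM and AUS in assessing FI". Section 5 describes a within-person design: "Through undertaking all three tests participants will act at their own controls". The schedule in Appendix 1 places the incontinence questionnaire, HRAM and MAPLe together at visit 2.

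**The concern.** The protocol argues for a new test because existing functional tests relate poorly to symptoms. It cites one study that "identified no correlation between ARP and FI scores in a study of 218 patients", and says that a second study, of 53 symptomatic women, agreed. The symptom component of benefit speaks most directly to that argument, yet it has no comparator inside the trial.

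A MAPLe correlation alone is hard to read in either direction. A clear one may occur in a group where HRAM tracks symptoms equally well or better. A weak one may occur where HRAM does worse still. The cited studies cannot fill the gap: they come from other cohorts, and a reported lack of correlation there does not establish a correlation of zero here.

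**Working it through.** **1. The plan's own figure.** Section 11.3 gives 30 participants in each of 4 groups: 4 × 30 = 120, which reproduces. The 30 cannot be derived, because no alpha, power, effect size or margin is stated.

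**2. Where each pairing is planned.**

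| Pairing | Planned? | Place |
|---|---|---|
| Symptoms with MAPLe | Yes | 11.1; section 5; Rationale |
| MAPLe with HRAM | Yes | 11.5.1 |
| Symptoms with HRAM | Not named | none |
| HRAM+AUS against MAPLe+AUS | Yes, on diagnosis, treatment and confidence | section 5, expert panel |

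**3. What a MAPLe-only correlation can miss.** All correlations from here on are assumptions, oriented so that positive means weaker function goes with worse symptoms. The approximate smallest r that reaches two-sided 5% significance is tanh(1.96/√(n−3)).

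- n=30: tanh(1.96/√27) = 0.36
- n=120: tanh(1.96/√117) = 0.179

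Take true symptom correlations of 0.3 (MAPLe) and 0.5 (HRAM), and 0.5 between the tests. Simulation of trivariate normal data (20,000 replicates) gives:

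| | n=30 | n=120 |
|---|---|---|
| MAPLe correlation significantly positive | 37% | 92% |
| Of those, HRAM has the larger sample correlation | 77% | 99% |
| Paired test rejects equal correlations | 21% | 69% |

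The first row is essentially unchanged (36% to 37%, and 92%) if HRAM's true correlation is 0.3 or 0 instead. The planned quantity therefore carries no information on relative performance.

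**4. Precision of the missing comparison.** For two correlations that share the symptom score, the Meng-Rosenthal-Rubin standard error on the Fisher z scale is √[2(1−r_x)h/(n−3)]. Here r_x is the inter-test correlation, h = (1−f·m)/(1−m), m is the mean of the two squared symptom correlations, and f = (1−r_x)/[2(1−m)], capped at 1.

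With both symptom correlations 0.3 and r_x = 0.5:

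- m = 0.09
- f = 0.5/1.82 = 0.275
- h = (1 − 0.275 × 0.09)/0.91 = 1.072
- n=120: SE = √(1.072/117) = 0.096, and 1.96 × 0.096 = 0.188. Multiplying by (1 − 0.09) to return to the r scale gives 0.17.
- n=30: SE = √(1.072/27) = 0.199, giving 0.39, or 0.355 on the r scale.

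| r_x | 95% half-width, n=30 | 95% half-width, N=120 |
|---|---|---|
| 0.2 | 0.45 | 0.21 |
| 0.5 | 0.355 | 0.17 |
| 0.7 | 0.28 | 0.13 |

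Over the same range of r_x, power to separate 0.4 from 0.1 is 25% to 55% at n=30 and 77% to 99% at N=120. For 0.3 against 0.1 it is 13% to 28% and 42% to 82%.

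**5. Equal correlation is not redundancy.** With two predictors of equal symptom correlation r, R² = 2r²(1−r_x)/(1−r_x²). At r_x = 0.5:

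- r = 0.3: 0.09/0.75 = 0.12, against 0.09 for HRAM alone.
- r = 0.4: 0.16/0.75 = 0.213, against 0.16 for HRAM alone.

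The added-value question therefore needs a regression on both tests as well as a difference in correlations.

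**The case against.** The strongest reply is that the primary outcome asks which groups benefit, not which test is better, and that comparison is supplied elsewhere. The panel's first question asks what MAPLe adds after HRAM and AUS, and its second sets HRAM+AUS against MAPLe+AUS. This stands in part: the primary outcome as a whole does have a comparator. But the panel assesses diagnosis, treatment and confidence, not symptom tracking.

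The open-ended correlation and regression work in 11.5.1 could also include HRAM. Nothing excludes it, but nothing commits to it, and a choice made after seeing the data would be post hoc.

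Three stronger readings are tempting, and the documents do not support them:

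- A reader might infer that a significant MAPLe correlation alone would be declared benefit, or a weak one held against the device. Section 11.1 sets no significance rule or threshold and lists two other components.
- A reader might infer that equal symptom correlations mean MAPLe adds nothing to HRAM. Step 5 shows otherwise, and equal tracking would also fit the Rationale's definition of non-inferiority.
- A reader might want benefit in each group decided by the paired difference. At n=30 the interval is too wide for that.

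Finally, the criterion speaks of a symptom profile, and the Rationale lists FI scores separately. Using the St Mark's score for this component is an assumption that the plan should settle.

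**Conclusion.** The gap is real and limited to the symptom-correlation component of benefit. Followed as written, that component cannot place MAPLe above, level with or below HRAM in tracking symptoms, although the paired data will exist. In the illustrative case where HRAM is truly better (0.5 against 0.3), MAPLe's correlation would look convincing in about 37% of groups of 30 and 92% of samples of 120, and the planned analysis would not reveal HRAM's advantage.

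These figures rest on assumed correlations, approximate normality and complete data on all three measures. The 120-person figures are pooled, whereas the plan describes the symptom correlation by group. The plan should be changed on this point, but it does not invalidate the other components of the primary outcome.

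**What to change.** In 11.1 and 11.5.1, name the symptom score and pre-specify, for the same participants and matching manoeuvres:

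- The MAPLe-symptom and HRAM-symptom correlations, rank-based if the ordinal score calls for it. Squeeze, endurance squeeze, push and cough appear in both test protocols in the appendices.
- Their paired difference with a 95% confidence interval, by bootstrap or a dependent-correlation method.
- A regression of the symptom score on both tests, to show what MAPLe adds to HRAM.

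Interpret the symptom component beside this comparison. Make the pooled N=120 estimate the main one and report the four groups descriptively. If the report is to say that MAPLe tracks symptoms no worse than HRAM, state a margin for the difference in advance.

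The cost is protocol wording and one extra analysis of data already collected, with no added visit or procedure. The downside is that a positive claim becomes harder to make, and even the pooled estimate will leave small differences unresolved.
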